4.1.1. Sample Size Re-Assessment

Sample size re-assessment procedures are described in section 4.3.

4.2. General Statistical Methods and Data Handling

4.2.1. General Methods

All output will be incorporated into Microsoft Excel or Word files, sorted and labeled according to the International Conference on Harmonisation (ICH) recommendations, and formatted to the appropriate page size(s).

Tabulations will be produced for appropriate demographic, baseline, efficacy, and safety parameters. For categorical variables, summary tabulations of the number and percentage within each category (with a category for missing data) of the parameter will be presented. For continuous variables, the mean, median, standard deviation, minimum and maximum values will be presented. Time to event data will be summarized using Bayesian Kaplan-Meier estimates.

Bayesian bivariate analysis will be performed on secondary efficacy endpoints outlined in 2.5.1. Summary statistics will be presented, as well as their corresponding 95% credible intervals.

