2.4. Study Procedures

As outlined in the study protocol, the schedule of assessment is provided in Table 1.

Statistical Analysis Plan

Sponsor:	McMaster University		
Protocol:	TOGETHER trial		
Document Version No.:	1.1	Document Date:	05-May-2021

Table 1. Schedule of Study Activities

	Screening and Treatment Period ⁹								Post-treatment Period ⁹			
	Screening Visit (D-0)	Baseline and Randomization (1) D-0	Day 1	Day 2 ⁽⁴⁾	Day 3 ⁽⁴⁾ ± 1 day	Day 4 ⁽⁴⁾	Day 5 ⁽⁴⁾	Day 7 ⁽⁴⁾ ± 1 day	Day 10 ± 2 days	Day 14 ⁽⁴⁾ ± 2 days	Day 28 ⁽⁴⁾ ± 3 days	Day 60 ^(4,8) or Early Termination ± 5 days
Informed Consent	X											
SARS-CoV2 Rapid Test	X ⁽¹⁾											
Eligibility Criteria Review	X ⁽²⁾											
Pregnancy Test	X ⁽³⁾											
Demographics	X ⁽⁵⁾											
Co-morbidities and Risk Factors	X											
Medical History	X											
WHO Clinical Worsening Scale	X		X	X	X	X	X	X	X	X	X	X
Temperature, Arterial O ₂ Saturation		X										
Exposure to Index Case Information		X										
Substance Abuse		X										
PROMIS Global Health Scale		X ⁽⁶⁾								X ⁽⁶⁾	X ⁽⁶⁾	X ⁽⁶⁾
ECG		X										
Height and Weight		X										
Nasopharyngeal Swab		X			X			X				
Randomization		X										
Concomitant Medications		X	X	X	X	X	X	X	X	X	X	X
Investigational Treatment Administration			X ⁽⁷⁾	X ⁽⁷⁾	X ⁽⁷⁾	X ⁽⁷⁾	X ⁽⁷⁾	X ⁽⁷⁾	X ⁽⁷⁾			

Statistical Analysis Plan

Sponsor:	McMaster University		
Protocol:	TOGETHER trial		
Document Version No.:	1.1	Document Date:	05-May-2021

Hospitalization / Emergency Room Visits			X	X	X	X	X	X	X	X	X	X
Respiratory Symptoms			X	X	X	X	X	X	X	X	X	X
Adverse Events			X	X	X	X	X	X	X	X	X	X
Adverse Drug Reactions			X	X	X	X	X	X	X	X	X	X
Vaccination Status										X	X	X

Legend

1. Screening and baseline visit: must be carried out at the same time when attending the outpatient setting. Rapid antigen test for COVID-19 at the screening visit. Day 1 visit should also be conducted on the same day as the screening and baseline visit. After completing the screening visit procedures at the baseline visit and present all inclusion / exclusion criteria, participants should be immediately randomized. The first dose of treatment under investigation must be administered on the same day of randomization (immediately after randomizing). The study medication will be administered as prescribed. Patients must be observed for 30 minutes after the medication administration.

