2.5. Efficacy and Safety Variables

2.5.1. Efficacy Variables

Primary endpoint:

- Emergency room visit due to the clinical worsening of COVID-19 (defined as participants remaining under observation for > 6 hours) within 28 days of randomization
- Hospitalization due to the progression of COVID-19 (defined as worsening of viral pneumonia) and/or complications within 28 days of randomization

Secondary endpoints:

- Viral clearance and viral load on D3 and D7 after randomization;
- Time (in days) to clinical improvement (up to 28 days of randomization), defined as the first day on which the participants report a score of 0 on the World Health Organization (WHO) Clinical Worsening Scale;
- Time (in days) to clinical failure;
- Number of days with respiratory symptoms since randomization;
- Hospitalization for any causes;
- Time to hospitalization due to COVID-19 progression;
- Mortality due to pulmonary complications;
- Mortality due to cardiovascular complications;
- Mortality from any causes;
- Adverse events that occurred (up to 28 days);
- Adverse drug reactions;
- WHO clinical worsening scale over the follow-up period;
- WHO clinical worsening scale during the treatment phase;
- PROMIS global health scale scores (days 14 and 28).

Statistical Analysis Plan

Sponsor:	McMaster University		
Protocol:	TOGETHER trial		
Document Version No.:	1.1	Document Date:	05-May-2021

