4.2.3. Statistical Analysis Details

4.2.3.1. Bayesian inference for dichotomous outcomes with covariate adjustment

Here we may use the generalized linear model framework for binary outcome with the logistic link function, namely

$$y_i \sim \text{Binom}(1, p_i)$$

with

$$\log \frac{p_i}{1 - p_i} = x_i^T \beta + \gamma T_i,$$

using the same notations as before. Assigning a noninformative prior distribution $p(\beta, \gamma) \propto 1$, the logarithm of the posterior distribution (after some simple algebra) is given by

$$\begin{aligned} \log p(\beta, \gamma | \mathbf{y}) &= \log p(\beta, \gamma) + \sum_{i=1}^n \log p(y_i | \beta, \gamma) \\ &= \sum_{i=1}^n \{y_i(x_i^T \beta + \gamma T_i) - \log[1 + \exp(x_i^T \beta + \gamma T_i)]\}, \quad (1) \end{aligned}$$

and a random sample from $p(\beta, \gamma | \mathbf{y})$ may then be drawn using Markov Chain Monte Carlo (MCMC) such as the Metropolis-Hastings algorithm¹ using (5) or Gibbs sampling using any software for Hierarchical Bayesian modeling such as BUGS² or JAGS³. Inference on the treatment effect will then follow the same procedure as in the numeric case.

The treatment effects on dichotomous outcomes will be estimated using R.

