4.6. Efficacy Evaluation

Efficacy analysis will be conducted using the ITT and PP Populations as outlined below. The two primary endpoints will be analyzed as a composite. Secondary endpoints will be assessed within 28 days of randomization, unless stated differently.

Table 3: Objectives and Endpoints

Objectives	Endpoints
Primary	

 Reduction in the need for emergency room visits due to the clinical worsening of COVID-19 and keeping the participant under observation for > 6 hours within 28 days of randomization in acutely affected patients and with evidence of high-risk for complications 	
 Proportion of those in need of emergency care under observation for more than 6 hours for COVID-19

 Reduction in the need for hospitalization due to the progression of COVID-19 (worsening of viral pneumonia) or complications within 28 days of randomization in acutely affected patients and with evidence of high-risk for complications 	
 Proportion of those in need of hospitalization due to progression of COVID-19 and/or complications
Secondary	

 To test the efficacy of experimental interventions to reduce SARS-CoV-2 viral shedding at day 3 and day 7 	
 Proportion of persons with clearance of SARS-CoV-2 from nasal swabs or saliva, defined as 1 negative swab Proportion of days with SARS-CoV-2 detected from mid-nasal swabs by PCR Change in viral load on day 3 and day 7 compared to baseline

 To test whether any of the experimental interventions decrease time to resolution for symptomatic SARS-CoV-2 infection / COVID-19 disease 	
 Time to clinical improvement (up to 28 days of randomization), defined as the first day on which the participant reports a score of 0 on the WHO Clinical Worsening Scale

Statistical Analysis Plan

Sponsor:	McMaster University		
Protocol:	TOGETHER trial		
Document Version No.:	1.1	Document Date:	05-May-2021

	
 • Time to clinical failure • Number of days with respiratory symptoms after randomization • Proportion of patients on each scale of the WHO clinical worsening scale over the treatment period and over the follow-up period

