
 • To test whether any of the experimental interventions is associated with decreased mortality within 28 days of randomization 	
 • Proportion of participants who died due to any cause • Proportion of participants who died due to pulmonary complications • Proportion of participants who died due to cardiovascular complications

 • To test whether any of the experimental interventions is associated with decreased hospitalization for any causes 	
 • Proportion of participants hospitalized due to any cause

 • To test whether any of the experimental interventions is associated with the time of hospitalization due to COVID-19 	
 • Time to hospitalization due to COVID-19 progression

 • To test the quality-of-life (QoL) of experimental interventions for treatment of high-risk outpatients with SARS-CoV-2 infection 	
 • Change in quality of life measured by PROMIS Global-10 from baseline to Day 14 and Day 28

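### The SAP writes no model for viral load and PROMIS; its only stated method, an undefined bivariate analysis, would in its ordinary sense leave the collected baseline values out as covariates and lose precision

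*SAP*

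**What the plan says.** - **Method.** SAP section 4.2.1: "Bayesian bivariate analysis will be performed on secondary efficacy endpoints outlined in 2.5.1". The term is not defined, and no covariate or baseline term is named. The section adds summary statistics with 95% credible intervals.
- **Endpoints, first list.** Section 2.5.1 gives "Viral clearance and viral load on D3 and D7 after randomization", and PROMIS as scores on days 14 and 28. Both are values on given days.
- **Endpoints, second list.** Table 3 in section 4.6 gives "Change in viral load on day 3 and day 7 compared to baseline" and "Change in quality of life measured by PROMIS Global-10 from baseline to Day 14 and Day 28". Both are changes.
- **Models.** Section 4.2.3.1 opens with "Here we may use the generalized linear model framework for binary outcome with the logistic link function", and section 4.2.3.2 sets out a proportional hazards model. Both carry covariates. No model is written for a continuous outcome. Section 4.2.3.1 nevertheless says that inference follows a procedure for numeric outcomes, relies on notation said to be introduced earlier, and cites an equation (5) that does not appear there.
- **Data.** In the schedule (section 2.4), the "Nasopharyngeal Swab" row is marked at baseline, day 3 and day 7. The "PROMIS Global Health Scale" row is marked at baseline and days 14, 28 and 60.
- **Missing data.** Section 4.2.7 allows multiple imputation of baseline covariates with up to 20% missing values, and none for outcomes.

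**The concern.** Viral load and PROMIS are the continuous secondary endpoints with a baseline measurement of the same quantity. An analyst who follows section 4.2.1 literally would compare arms on the outcome alone. That outcome could be the follow-up value (2.5.1) or the change (Table 3), because the SAP supports both. Neither comparison uses the baseline value as efficiently as a model that includes it as a covariate, so the credible intervals would be wider than the data require. The choice between value and change would also be open after the data are seen.

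The missing-data rule adds a smaller point. If the outcome is a change, a missing baseline makes the outcome missing, and section 4.2.7 forbids imputing it. If baseline is a covariate in a model for the follow-up value, the same section allows it to be imputed and the patient stays in.

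**Working it through.** The SAP states no SD, correlation, effect size or power for these endpoints, so there is no figure of its own to reproduce. The check compares the variance of the treatment contrast under three analyses.

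**Inputs**
- Sample size: 681 per arm (section 4.1), used only for scale.
- Correlation rho between baseline and follow-up: not in the SAP; assumed range 0.2 to 0.8.
- SDs at baseline (s0) and follow-up (s1): not in the SAP; assumed equal for the figures.

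**Formulas** (large samples, common factor 2/n omitted)
- Follow-up value alone: s1²
- Change score: s0² + s1² − 2·rho·s0·s1
- Baseline-adjusted: s1²(1 − rho²)

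Change score minus adjusted is (s0 − rho·s1)². Follow-up alone minus adjusted is rho²·s1². Neither can be negative, so the direction does not depend on equal SDs; only the size does. With s0 = s1 = 1:

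| rho | Follow-up | Change, 2(1 − rho) | Adjusted, 1 − rho² | Adjusted / change | Adjusted / follow-up |
|---|---|---|---|---|---|
| 0.2 | 1 | 1.60 | 0.96 | 0.60 | 0.96 |
| 0.3 | 1 | 1.40 | 0.91 | 0.65 | 0.91 |
| 0.5 | 1 | 1.00 | 0.75 | 0.75 | 0.75 |
| 0.7 | 1 | 0.60 | 0.51 | 0.85 | 0.51 |
| 0.8 | 1 | 0.40 | 0.36 | 0.90 | 0.36 |

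At rho 0.3, 0.5 and 0.7 the variance saving is therefore 35%, 25% and 15% against a change score, and 9%, 25% and 49% against the follow-up value. The two series move in opposite directions and meet at 0.5, so the size of the loss depends on which endpoint list is followed.

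**In patients.** At rho 0.5, 681 per arm with adjustment has the precision of 681/0.75 = 908 per arm without it, on either endpoint definition. At rho 0.3 the unadjusted equivalents are 681/0.65 = 1048 (change) and 681/0.91 = 748 (follow-up). At rho 0.7 they are 681/0.85 = 801 and 681/0.51 = 1335.

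**In power.** For an assumed true difference of 0.15 SD, 681 per arm and two-sided 0.05:

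| rho | Follow-up | Change | Adjusted |
|---|---|---|---|
| 0.2 | 79% | 59% | 81% |
| 0.5 | 79% | 79% | 89% |
| 0.8 | 79% | 99.2% | 99.6% |

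The gain is small against a change score when rho is high, and small against the follow-up value when rho is low.

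**The case against.** The strongest reply is that the SAP never calls these analyses unadjusted. Section 4.2.1 applies *bivariate* to all secondary endpoints in 2.5.1. Every time-to-event endpoint there is secondary, yet section 4.2.3.2 gives time-to-event outcomes a covariate-adjusted model, so in this document the word coexists with adjustment. The dangling references in 4.2.3.1 suggest that an adjusted numeric-outcome section was intended and left out, and 4.2.7 foresees adjustment for baseline covariates in general terms. Table 3 names endpoints, not models, and a change can itself be modelled with baseline as a covariate. In a linear model that gives the same treatment effect as modelling the follow-up value.

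All of this stands. A reader might infer that the sponsor deliberately chose an unadjusted analysis of change scores; the SAP does not support that. It leaves the term undefined, the numeric model unwritten and the endpoint stated two ways.

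A reader might also infer that baseline information is thrown away altogether, or that the results would be biased. A change score already uses baseline, though inefficiently; baseline is wholly ignored only if the day-specific values of 2.5.1 are compared without adjustment. Under randomisation both unadjusted contrasts are unbiased over repeated allocations. Chance baseline imbalance is part of the variances above and should not be counted a second time.

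What the reply does not do is supply a model. The only method the SAP states for these two endpoints names no baseline term.

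**Conclusion.** The point holds as a gap in specification with a cost in precision. Taken in its ordinary sense, the one stated method is less precise than a baseline-adjusted model, whether values or changes are analysed, for any positive correlation below 1 with equal SDs. Over the assumed range 0.2 to 0.8, the unadjusted variance is 1/0.90 = 1.11 to 1/0.60 = 1.67 times the adjusted variance for a change score, and 1/0.96 = 1.04 to 1/0.36 = 2.78 times for the follow-up value.

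These sizes rest on assumed correlations and equal SDs. Undetectable results on day 3 or day 7 could make the equal-SD assumption poor for viral load. Nothing here affects the primary composite or the stopping rules in section 4.3, which rest on a binary outcome. The change should be made, but the trial's main conclusion does not depend on it.

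**What to change.** 1. Add the numeric-outcome section to 4.2.3: a Bayesian linear model for log10 viral load on day 3 and day 7, and for PROMIS on day 14 and day 28, with arm, the baseline value of the same measure, and the randomisation factors from section 2.2 (site, age group, time from symptom onset). Use the follow-up value as the outcome, so that the imputation rule in 4.2.7 can apply to a missing baseline.
2. State how undetectable viral loads enter the model, at baseline and at follow-up.
3. Align section 2.5.1 with Table 3, so that each endpoint has one definition.
4. Define *bivariate* in 4.2.1 and limit it to descriptive two-arm summaries.
5. Point the orphaned references in 4.2.3.1 to the new section.

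The cost is SAP wording and one decision on undetectable values. The baseline swab and baseline PROMIS are already scheduled, so no new data, visits or patients are needed.

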4.2.2. Computing Environment

All descriptive statistical analyses will be performed using SAS statistical software (Version 9.4), unless otherwise noted. Medical History and adverse events will be coding using MedDRA version 23.0. Concomitant medications will be coded using World Health Organization (WHO) Drug dictionary (version March 1, 2020).

Statistical Analysis Plan

Sponsor:	McMaster University		
Protocol:	TOGETHER trial		
Document Version No.:	1.1	Document Date:	05-May-2021

4.2.3. Statistical Analysis Details

4.2.3.1. Bayesian inference for dichotomous outcomes with covariate adjustment

Here we may use the generalized linear model framework for binary outcome with the logistic link function, namely

$$y_i \sim \text{Binom}(1, p_i)$$

with

$$\log \frac{p_i}{1 - p_i} = x_i^T \beta + \gamma T_i,$$

using the same notations as before. Assigning a noninformative prior distribution $p(\beta, \gamma) \propto 1$, the logarithm of the posterior distribution (after some simple algebra) is given by

$$\begin{aligned} \log p(\beta, \gamma | \mathbf{y}) &= \log p(\beta, \gamma) + \sum_{i=1}^n \log p(y_i | \beta, \gamma) \\ &= \sum_{i=1}^n \{y_i(x_i^T \beta + \gamma T_i) - \log[1 + \exp(x_i^T \beta + \gamma T_i)]\}, \quad (1) \end{aligned}$$

and a random sample from $p(\beta, \gamma | \mathbf{y})$ may then be drawn using Markov Chain Monte Carlo (MCMC) such as the Metropolis-Hastings algorithm¹ using (5) or Gibbs sampling using any software for Hierarchical Bayesian modeling such as BUGS² or JAGS³. Inference on the treatment effect will then follow the same procedure as in the numeric case.

The treatment effects on dichotomous outcomes will be estimated using R.

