4.2.3.2. Bayesian inference for time-to-event outcomes with covariate adjustment

We assume here that the data satisfies the Cox proportional hazards assumption, that is –

$$\log h(t; x, T, \beta, \gamma) = \log h_0(t) + x^T \beta + \gamma T,$$

where $h_0(t)$ is the baseline hazard function and $h(t; x, T, \beta, \gamma)$ is the hazard function of an individual with covariate vector x who was assigned to treatment T , evaluated at time t .

We model the baseline hazard as a piecewise constant function

Statistical Analysis Plan

Sponsor:	McMaster University		
Protocol:	TOGETHER trial		
Document Version No.:	1.1	Document Date:	05-May-2021

$$h_0(t; \boldsymbol{\lambda}) = \sum_{j=1}^J \lambda_j \mathbb{I}(t \in (a_{j-1}, a_j]) \quad (1)$$

as in Ibrahim et al.⁴ for $\lambda_1, \dots, \lambda_J \geq 0$ and some partition $a_0 = 0 < a_1 < \dots < a_J = t_{max}$ of the real line with t_{max} the end of the follow-up period. This induces the baseline survival function

$$S_0(t; \boldsymbol{\lambda}) = - \sum_{j=1}^J \lambda_j (t - a_{j-1}) \mathbb{I}(t \in (a_{j-1}, a_j]), \quad (2)$$

and, denoting $\mathbf{t} = [t_1, \dots, t_n]^T$ the vector of event times, the log-likelihood function is given by

$$\ell(\mathbf{t}; \boldsymbol{\beta}, \gamma, \boldsymbol{\lambda}) = \sum_{i=1}^n [(1 - \delta_i) \log h_0(t_i; \boldsymbol{\lambda}) + x_i^T \boldsymbol{\beta} + \gamma T_i + \log S_0(t_i; \boldsymbol{\lambda}) + \exp(x_i^T \boldsymbol{\beta} + \gamma T_i)], \quad (3)$$

where δ_i is an indicator assuming the value of 1 if the i^{th} observation was right-censored and 0 otherwise. We may then assign an improper, independent prior $p(\boldsymbol{\beta}, \gamma, \boldsymbol{\lambda}) \propto \prod_{j=1}^J \lambda_j^{-1}$, and proceed to generate an MCMC sample from the posterior distribution, using the log-posterior

$$\log p(\boldsymbol{\beta}, \gamma, \boldsymbol{\lambda} | \mathbf{t}) = \text{const} + \ell(\mathbf{t}; \boldsymbol{\beta}, \gamma, \boldsymbol{\lambda}) - \sum_{j=1}^J \log \lambda_j$$

within a Metropolis-Hastings scheme. Inference on treatment efficacy, as always, will be based on the $100(1 - \alpha)\%$ credible interval for γ .

The treatment effects on time-to-event outcomes will be estimated using R.

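### The covariate-adjusted models use improper priors with no fallback, so an arm with no events leaves the treatment effect without a valid posterior

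*SAP*

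**What the plan says.** Section 4.2.3.1 introduces the adjusted model for dichotomous outcomes in permissive terms: "Here we may use the generalized linear model framework for binary outcome with the logistic link function". The prior follows ("Assigning a noninformative prior distribution") and is written as p(beta, gamma) proportional to 1. The covariate vector is not defined there.

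Section 4.2.3.2 covers time-to-event outcomes: "We model the baseline hazard as a piecewise constant function". On the prior it says "We may then assign an improper, independent prior", which is flat on beta and gamma with a factor 1/lambda_j for each interval. The number of intervals and the cut-points are left open.

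Neither section states a condition for a proper posterior, or a fallback for an arm or interval with no events.

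Section 2.5.1 lists "Mortality due to cardiovascular complications" among the secondary endpoints. Section 4.6 defines the cause-specific deaths as proportions: "Proportion of participants who died due to pulmonary complications" and "Proportion of participants who died due to cardiovascular complications". They are therefore dichotomous. The time-to-event endpoints are clinical improvement, clinical failure and hospitalization due to COVID-19 progression.

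For secondary endpoints generally, section 4.2.1 says "Bayesian bivariate analysis will be performed on secondary efficacy endpoints outlined in 2.5.1", with 95% credible intervals; that analysis is not defined further. The stopping and final decision rule (section 4.3 and Appendix) uses a proper Beta(1,1) prior for each arm.

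**The concern.** A flat prior on a log-odds ratio or log-hazard ratio is harmless when both arms have events, because the likelihood then falls away in both directions. With no events in one arm it does not. As gamma goes to minus infinity (no events on treatment) or plus infinity (no events on control), the likelihood levels off at a positive constant. A flat prior times a constant has infinite mass, so no posterior exists.

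A sampler gives no reliable warning. Metropolis-Hastings or Gibbs output drifts along the flat direction, and the reported quantiles reflect the run length and starting values rather than the data. An interval for cardiovascular or pulmonary death could then be printed with nothing behind it, on endpoints that readers examine for benefit or harm. If the gap is noticed only after a zero cell appears, the replacement prior would be chosen with the result in view.

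**Working it through.** The SAP states no figure on this point, so there is none to reproduce. The check has two parts: whether the posterior exists, and how often the problem could arise.

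**Inputs.** From the SAP: the priors (4.2.3.1, 4.2.3.2); 681 per arm at full enrolment (4.1); 171, 342 and 513 per arm at the interim analyses (Appendix); a 15% control rate and 37.5% relative reduction for hospitalization (4.1). Assumed: the death rates, because the SAP gives none, and the illustrative event counts. For the hazard model the standard piecewise-exponential likelihood was used, because the baseline survival function as printed in equation (2) is negative.

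**1. Logistic model, flat prior, intercept plus treatment, control 3/681.** Integrate the unnormalised posterior over |gamma| < 10, 20, 40 and scale to the first value.
- Treatment 0/681: 1.00, about 2.2, about 4.5. The mass keeps growing with the range, so the posterior is improper.
- Treatment 1/681: 1.00, 1.00, 1.00. One event is enough.

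**2. Proportional hazards model, one interval, equal exposure.** After integrating out lambda, the marginal for gamma is proportional to exp(gamma·d1)/(1 + exp(gamma))^(d0+d1). Integrate over |gamma| < 10, 20, 40, 80.
- d0 = 3, d1 = 0: 8.5, 18.5, 38.5, 78.5. Improper.
- d0 = 3, d1 = 1: 0.333 throughout. Proper.

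**3. Chance of an event-free arm.** With true rate p in both arms and n per arm, q = (1 − p)^n, and the chance that at least one of two arms has no events is 1 − (1 − q)². For n = 681 and p = 0.1%: q = 0.999^681 = 0.506, and 1 − 0.494² = 0.76.

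| n per arm | 0.1% | 0.2% | 0.5% | 1% |
|---|---|---|---|---|
| 681 | 76% | 45% | 6.5% | 0.2% |
| 513 | 84% | 59% | 15% | 1.2% |
| 342 | 92% | 75% | 33% | 6.3% |
| 171 | 98% | 92% | 67% | 33% |

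Setting the chance to 50% gives q = 1 − √0.5 = 0.293 and p = 1 − 0.293^(1/n): 0.18% at 681, 0.24% at 513, 0.36% at 342 and 0.72% at 171.

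**4. Empty interval (time-to-event endpoints only).** With no events in interval j, the factor for lambda_j is exp(−lambda·E)/lambda, where E is the exposure in that interval. Its integral from a lower limit of 1e-6, 1e-12, 1e-24, 1e-48 is 4.8, 18.6, 46.2, 101.5, so it diverges; with one event it converges. For time to hospitalization at 15% against 9.375% (15% × 0.625), spread evenly over 28 daily intervals (the spread and the cuts are assumptions), the chance of at least one empty interval is about 99.9% at 171 per arm, 77% at 342, 27% at 513 and 7% at 681.

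The divergence lies in lambda_j, not in gamma. With 100 against 65 events elsewhere (assumed counts), the 95% interval for gamma is −0.750 to −0.123 without the empty interval. It stays within 0.001 of that when the empty interval is included with lambda_j truncated anywhere from 1e-8 to 1e-200.

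**5. Event-free site, if site terms are used.** With 20 against 12 events in 640 per arm elsewhere and an empty site of 34 per arm (assumed), the interval for gamma is −1.299 to 0.177 without the site. It is the same with the site coefficient bounded at 1000, and −1.307 to 0.165 with it bounded at 10.

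**The case against.** The strongest reply is that little in the trial depends on this. The stopping and final rules use proper Beta(1,1) priors. Both adjusted models are worded as options, and for secondary endpoints section 4.2.1 names a different, undefined analysis, so the SAP does not firmly commit cause-specific deaths to the flat-prior model. An event-free arm would also be visible in the required tabulations of counts and percentages. All of this stands, and it keeps the severity low. It does not remove the gap: section 4.2.3.1 is the only covariate-adjusted model given for dichotomous outcomes, and its prior has no fallback.

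Three stronger readings are tempting, and the SAP does not support them.
- A reader might infer that failure is likely for the cause-specific mortality endpoints. The SAP gives no death rate. At 681 per arm, more likely than not requires a rate below about 0.18%; at 1% the chance is 0.2%.
- A reader might infer that the 1/lambda_j prior threatens the mortality results. Section 4.6 defines those endpoints as proportions, so the hazard model does not apply to them.
- A reader might infer that any empty interval or event-free site invalidates the treatment estimate. The joint posterior is formally improper, but the interval for gamma barely moves. Site is a randomization stratum in section 2.2; that it enters the model as fixed terms is an assumption.

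**Conclusion.** The point holds in a limited form. As written, both adjusted models give an improper posterior for gamma when a treatment arm has no events, and the SAP has no rule for that case. This is possible for rare dichotomous secondary endpoints such as cardiovascular death. How probable it is depends on a rate the SAP does not give. Under equal assumed rates the chance at 681 per arm runs from 76% at 0.1% down to 0.2% at 1%, and at 171 per arm it is still 33% at 1%. For the time-to-event endpoints, empty intervals are a formal defect with little effect on the treatment estimate. The primary decision rule is unaffected. This is a cheap improvement of minor severity.

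**What to change.** In section 4.2.3.1, replace the flat prior on gamma and the covariate coefficients with a proper weakly informative one, for example normal with mean 0 and SD 2.5 on the log-odds scale. In section 4.2.3.2, do the same on the log-hazard scale, and give each lambda_j a Gamma prior with positive shape. For cause-specific deaths, report the Beta-binomial comparison already in the Appendix; it is proper for any count, though not covariate-adjusted.

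Both routes work in the problem case of 0/681 against 3/681. The normal prior on gamma gives a median log-odds ratio of about −2.4, a 95% interval of about −6.1 to 0.2 and Pr(gamma < 0) = 0.965. Beta(1,1) gives Pr(efficacy) = 0.938. The two answers differ because the prior matters when an arm has no events, so the choice should be fixed before unblinding. The SD of 2.5 is one reasonable value among several.

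The cost is SAP wording and a few lines of code. The downside is slight shrinkage for rare outcomes.
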